4.5.1.4 Sensitivity Analyses

Sensitivity analyses will be performed to evaluate the robustness of the primary analysis results. Analyses will be performed for the overall patient population and/or the biomarker subgroup populations, as deemed appropriate based on the outcome of the primary analyses including all patients in the ITT population.

Multiple Imputation

The following sensitivity analysis based on multiple imputation will be performed, as appropriate, using the same statistical approach as the one used in the primary analysis:

- Change from baseline in GA area as measured using FAF, with missing data imputed by multiple imputation using the Markov Chain Monte Carlo (MCMC) method assuming MAR
- Change from baseline in GA area as measured using FAF, with missing data imputed by multiple imputation using regression method assuming MAR
- Change from baseline in GA area as measured using FAF, with missing data imputed by multiple imputation using pattern mixture model method assuming missing not at random (MNAR)
- Change from baseline in GA area as measured using FAF, with missing data imputed by multiple imputation using tipping point analysis method assuming MNAR

Considering the details of the four multiple imputation methods (MCMC, regression method, pattern mixture model, and tipping point analysis) further, MCMC and regression methods assume MAR, where the imputed data will follow the same distribution as the observed data within the same treatment group. Pattern mixture model and tipping point analysis methods assume MNAR, where the imputed data for the active treatment group will follow either the distribution of the control group or adjusted by a shift parameter.

Geographic atrophy is progressive and irreversible, so changes in GA area over time should be ≥ 0 mm². In order to incorporate this data pattern, imputation for missing data will be performed on the difference in GA area at a visit from the previous visit. Imputation for the non-monotone missing pattern (i.e., arbitrary missing pattern) will be performed prior to the multiple imputation for the monotone missing pattern (i.e., where a missing GA area measurement at a visit for a patient implies that GA area measurements at all subsequent visits for that patient are missing). For the non-monotone missing pattern, missing value(s) between two visits with measured GA area will be imputed according to a linear growth line passing through the two measured sizes. Multiple imputation will only be carried out for monotone missing pattern.

All four imputation methods will be implemented in SAS using the three standard steps to generate inference from imputed data: imputation step, analysis step, and pooling step.

1. The missing data are filled in 100 times to generate 100 complete data sets.
2. The 100 complete data sets are analyzed by using the same approach as for the analysis for the primary objective.
3. The results from the 100 complete data sets are combined for the inference.

Methods used in the imputation step are described below. The actual parameters used in all imputations will be documented in the programming specifications. Analysis and

pooling steps will be carried out following the imputation step will also be documented in the programming specifications.

- **MCMC Method.** The MCMC method will be implemented for each treatment arm (the two sham arms will be pooled) and by biomarker status.
- **Regression Method.** The regression method will be implemented for each treatment arm and by biomarker status. This method assumes MAR, and serves as the reference for the pattern mixture model and tipping point analysis methods which assume MNAR.
- **Pattern Mixture Model Method.** The pattern mixture model method will be implemented for each active treatment arm and by biomarker status. For the active treatment arms, the missing data will be imputed based on the observed values in the pooled sham arm.
- **Tipping Point Analysis Method.** The tipping point analysis method will be implemented for each active treatment arm and by biomarker status under the MNAR assumption by searching for a tipping point that reverses the conclusion regarding positive treatment effect. For the active treatment arms, monotone missing data will be imputed based on the available values (observed values plus values imputed for non-monotone missing data) in the same treatment arm with a shift parameter added to the imputed values. Multiple imputation will be implemented on the differences between two consecutive visits, with the shift parameter allocated to the missing data point(s) proportionally across the 48 weeks. (e.g. For a shift parameter of 1 mm², incremental shifts of 0.5 mm², 0.25 mm², and 0.25 mm² would apply to Week 24, Week 36, and Week 48, respectively.) The range of the shift parameters will depend on the observed treatment effect, i.e., the difference in the change of GA area from baseline at Week 48 between lampalizumab and the pooled sham arms. The precision of the tipping point will be at one decimal point. A tipping point may not exist within reasonable clinical assumptions.

Additional Sensitivity Analyses:

Moreover, the following sensitivity analysis will be conducted based on observed data for the primary endpoint:

- **ANCOVA:** Comparison of the mean change in GA area from baseline at Week 48 between each lampalizumab arm (Q4W or Q6W) and the pooled sham arm using an analysis of covariance (ANCOVA) regression model with change from baseline at Week 48 as the response variable and independent variables for treatment arm, baseline GA area, and the randomization stratification factors and baseline covariates as described in Section 4.5.
- **Van Elteren Test:** Comparison of the distribution of change in GA area from baseline at Week 48 between each lampalizumab arm (Q4W or Q6W) and the pooled sham arm respectively, using the non-parametric Van Elteren test stratified by baseline GA area ($\leq 4DA$, $> 4DA$, where 1 disc area [DA] = 2.54 mm²) and the randomization stratification factors and baseline covariates as described in Section 4.5.

4.5.1.5 Supplemental Analyses

Analyses of the following endpoints, closely related to the primary efficacy endpoint, will be performed to provide supplemental information. Analyses will be performed for the overall patient population and/or the biomarker subgroup populations, as deemed appropriate based on the outcome of the primary analyses.

Rate of Change in GA Area (Growth Slope) over 48 Weeks

The mean rate of change in GA area (mm^2/year [365.25 days]) will be compared between each lampalizumab treatment arm (Q4W or Q6W) and the pooled sham arm by use of a random intercept and random slope regression model. GA area (at baseline and post-baseline visits up to Week 48) will be used as the response variable, and the model will include terms for treatment arm, time (continuous variable assuming linearity), treatment arm by time interaction, and the randomization stratification factors and baseline covariates as described in Section 4.5. Random effects will include the intercept and slope (time) with an unstructured covariance matrix, with all other variables as fixed effects. The within patient error will be assumed to be independent and normally distributed with variance component as the covariance structure.

Change in Square Root of GA Area at Week 48

For each patient and timepoint, the square root of GA area will be calculated. The change from baseline in square root of GA area will be analyzed using the same methodology as described for the primary endpoint analysis, except that change from baseline in the square root of GA area will be the response variable.

Percent Change in GA Area at Week 48

For each patient and timepoint, the percent change in GA area will be defined as the change from baseline in GA area (mm^2) divided by the GA area (mm^2) at baseline. The percent change in GA area from baseline will be analyzed using the same methodology as described for the primary endpoint analysis, except that percent change from baseline will be the response variable. In addition, baseline GA area will not be included as a covariate in the model.

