6.1 DETERMINATION OF SAMPLE SIZE

Patients will be randomized in a 2:1:2:1 ratio to receive treatment with lampalizumab Q4W, sham Q4W, lampalizumab Q6W, or sham Q6W. Data from the two sham groups will be pooled in the analysis.

The study is sized to achieve adequate power for detecting a meaningful reduction rate in the GA area growth for a given lampalizumab dosing frequency compared with pooled sham within CFI profile biomarker-positive and CFI profile biomarker-negative groups and to meet health authority requirements for the safety database.

The primary endpoint is the mean change in GA area from baseline to 1 year as assessed by FAF. [Table 7](#) summarizes the power calculation and minimum detectable difference for this primary endpoint. Assuming a standard deviation of 2.51 mm² for the change from baseline in GA area at 1 year in biomarker-positive patients, 188 CFI profile biomarker-positive patients per lampalizumab treatment group and 94 CFI profile biomarker-positive patients per sham group will provide >95% power to declare a difference between each lampalizumab treatment group and the pooled sham for a targeted difference of 1.45 mm² (approximately 40% reduction relative to sham control) in the change from baseline in GA area at 1 year. Assuming a standard deviation of 1.68 mm² for the change from baseline in GA area at 1 year in CFI profile biomarker-negative patients, 124 CFI profile biomarker-negative patients per lampalizumab treatment group and 62 CFI profile biomarker-negative patients per sham group will

provide 80% power to detect a targeted difference of 0.66 mm² (approximately 40% reduction) between each lampalizumab treatment group and the pooled sham group in the change from baseline in GA area at 1 year. Calculations were based on two-sided t-test at the $\alpha=0.0495$ level (after adjustment for planned interim data reviews conducted by the iDMC prior to analysis of the primary efficacy endpoint; see Section 3.1.2), with the assumption of a 15% dropout rate by 1 year. Due to lack of reliable information to estimate the impact of partially missing data on the power, the power calculation is based on the analysis of data from the patients who complete the first year of the study. However, the primary analysis of the study will include all available data from patients in all treatment arms, which will have more power than an analysis of just those patients completing the first year of the study period.

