2.1.4 Supplemental Efficacy Endpoints Related to Primary Endpoint

The following efficacy endpoints, closely related to the primary efficacy endpoint, will be assessed over time up to Week 48 to provide supplemental information to the primary endpoint analysis. The endpoints will also be assessed over time up to Week 96 at the time of the final study analysis.

- Rate of change in GA area (growth slope) as assessed by FAF
- Change from baseline in square root of GA area as assessed by FAF
- Percent change from baseline in GA area as assessed by FAF

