2.3 SAMPLE SIZE

2.3.1 Determination of Sample Size

Approximately 936 patients will be enrolled in the study. Patients are randomized in a 2:1:2:1 ratio to receive treatment with lampalizumab Q4W, sham Q4W, lampalizumab Q6W, or sham Q6W. Data from the two sham treatment arms will be pooled in the analysis.

The study was originally sized to achieve adequate power for detecting a meaningful reduction rate in the GA area growth for a given lampalizumab dosing frequency compared with pooled sham within each of the biomarker-positive and biomarker-negative groups and to meet health authority requirements for the size of the safety database. At the time of the study design, sample size and power calculations used assumptions based on results from the Phase II Study CFD4870g. For details of the determination of sample size, see study protocol Section 6.1.

As outlined in Section 6.1, the protocol also specified that the Sponsor may conduct a masked evaluation of the variance of the primary efficacy endpoint and study dropout rate before the end of enrollment, with the intent to potentially increase the study sample size if deemed necessary in order to maintain the desired study power. However, such an evaluation was not conducted and the sample size of the study remained unchanged from that originally planned.

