2.3.2 Estimated Power Based on Information from Study GX29633

The primary efficacy endpoint is the change from baseline in GA area at 1 year (48 weeks) as assessed by FAF. As specified in Section 4.5.1, the primary efficacy objectives will be assessed by analysis of the primary efficacy endpoint in the overall patient population and in the biomarker-positive group for each dosing frequency separately.

[Table 2](#) summarizes the power and minimum detectable difference for the primary endpoint analysis when evaluated for the overall patient population and the biomarker-positive group using progression rates and variability assumptions based on data from Study GX29633, a prospective epidemiological study of the progression of GA secondary to AMD (May 2017 interim analysis). Namely, calculations assumed a progression rate (mean change from baseline in GA area at 48-weeks) of 2.08 mm² for both the biomarker-positive and biomarker-negative patient groups and a SD of 1.53 mm² for the change from baseline in GA area at 48-weeks. With these assumptions, 312 patients per lampalizumab treatment arm and 156 patients per sham arm will provide 88% power to declare a difference between each lampalizumab treatment arm and the pooled sham arm in the overall patient population for a targeted difference of 0.42 mm² (approximately 20% reduction relative to sham control) in the change from baseline in GA area at 48 weeks ([Table 2](#)). Estimated power to detect specified differences in the primary efficacy endpoint within the biomarker-positive

patient population is as shown in Table 2. Calculations were based on two-sided t-tests at the $\alpha=0.0496$ level (after adjustment for the four data reviews conducted by the iDMC prior to analysis of the primary efficacy endpoint), with the assumption of a 15% dropout rate by 48 weeks.

Table 2 Power and Minimum Detectable Difference for Analysis of Primary Endpoint Using Assumptions Based on the Epidemiological Study GX29633

Endpoint Summary and Population	Target Treatment Effect	Two-Sided $\alpha=0.0496$	
		Power	MDD
Mean change from baseline in GA area at 1 year (48 weeks) in all patients (n=312 per arm)	$\Delta=0.42 \text{ mm}^2$ (approximately 20% ^a reduction) SD= 1.53	88%	0.26 mm^2 (approximately 13% ^a reduction)

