4.5.1.1 Overall Patient Population Analysis

For the overall patient population, the mean change in GA area from baseline at Week 48 will be compared between each lampalizumab treatment arm (Q4W or Q6W) and the pooled sham arm by use of a MMRM analysis. The primary analysis will be based on all available data up to Week 48, with no imputation for missing data. The model will use absolute change from baseline in GA area at post-baseline visits, up to and including 48-weeks, as the response variable, and will include independent variables for treatment arm, study visit, treatment arm by study visit interaction, baseline GA area, and the randomization stratification factors and baseline covariates as

described in Section 4.5. Study visit will be included as a categorical variable. An unstructured covariance matrix will be used to model the within-subject errors. If there are convergence problems with the model, then a heterogeneous compound symmetry covariance structure will be used.

Point estimates, 95% CIs, and p-values for the treatment effect (difference in mean change in GA area from baseline for lampalizumab vs. sham pooled) will be calculated for each lampalizumab treatment arm on the basis of the model for each assessed timepoint, including Week 48.

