For the analysis of the proportion of patients with <20% increase in GA area, patients with missing GA assessment at the analysis timepoint (e.g. Week 48) will be included in the analysis and counted as having a $\geq 20\%$ increase if such an outcome was observed at any earlier timepoint.

Reading function scores will be calculated per MNRead or Radner user's manuals, with no adjustment for reading inaccuracy. For reading function endpoints (maximum reading speed, critical print size, and reading acuity), data collected via the two reading charts will be pooled for analysis and the model will include an additional covariate for reading chart type (MNRead or Radner). Additional subgroup analyses by reading chart type (MNRead or Radner) will be performed to assess the consistency of findings across the two reading charts. In addition, for analyses based on percent change in reading speed, the baseline reading speed will not be included in the model.

FRI Level will be calculated per the scoring algorithm in the FRI Index user's manual.

For analyses of binocular maximum reading speed, binocular critical print size, and binocular reading acuity, an additional adjustment for better seeing eye BCVA at baseline will be included (instead of study eye baseline BCVA [20/50 or better vs. worse than 20/50]).

In addition, the relationship between GA area and visual function outcomes (e.g. LLVA etc.) will be explored. Observed data will be used. Spearman correlation coefficient will be estimated and a 95% CI for the correlation coefficient provided.

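### Percent-change models leave out the baseline value and the growth-slope model lets no covariate act on slope: a possible loss of precision in supplemental and exploratory analyses only

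*SAP*

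**What the plan says.** SAP Section 2.1.4 lists growth slope, change in square root of GA area and percent change in GA area as endpoints that "will be assessed over time up to Week 48 to provide supplemental information to the primary endpoint analysis".

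- **Percent change in GA area (SAP 4.5.1.5).** The primary method is reused with percent change as the response, and then: "In addition, baseline GA area will not be included as a covariate in the model". The primary model it borrows (SAP 4.5.1.1) includes "treatment arm by study visit interaction, baseline GA area, and the randomization stratification factors" among its terms.
- **Percent change in reading speed (SAP 4.5.3).** Here "for analyses based on percent change in reading speed, the baseline reading speed will not be included in the model". These endpoints, binocular and monocular, are exploratory (SAP 2.1.3).
- **Growth slope (SAP 4.5.1.5).** This is a random intercept and slope model with GA area at baseline and later visits as the response. Its fixed terms are treatment arm, time, "treatment arm by time interaction, and the randomization stratification factors and baseline covariates as described in Section 4.5". No other product with time is listed.

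The baseline value is kept in the primary model, the ANCOVA sensitivity analysis (SAP 4.5.1.4), the square-root analysis and the continuous secondary models (SAP 4.5.2). The last group includes absolute change in binocular reading speed, which is tested as H07.

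**The concern.** Dividing by baseline removes the dependence on baseline only if change is proportional to baseline. The SAP does not claim this for GA area or for reading speed. If growth is less than proportional, small lesions produce large percentages. That predictable spread goes into the residual when baseline is left out.

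In the slope model the treatment effect is the treatment-by-time term. Covariates entered as main effects explain differences in level, not in growth rate. Sex is a stratification factor, and Protocol Section 3.3.2.1 links it to the rate of GA progression. The planned model contains sex but cannot use that link.

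What is at stake is interval width: these analyses may report wider intervals than the collected data require.

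**Working it through.** **1. The plan's own figure.** The SAP gives no precision figure for these models. The nearest is the overall-population power in SAP 2.3.2, where "calculations assumed a progression rate (mean change from baseline in GA area at 48-weeks) of 2.08" mm², with SD 1.53 mm², two-sided alpha 0.0496 and 15% dropout.

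- Patients per group: 312 × 0.85 = 265.2.
- SE = 1.53 × √(2/265.2) = 0.1329 mm².
- Power = Φ(0.42/0.1329 − 1.963) = Φ(1.198) = 88.4%, against 88% stated.
- Minimum detectable difference = 1.968 × 0.1329 = 0.26 mm², as stated.

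**2. Percent change in GA area.** From the documents: mean 2.08 and SD 1.53 mm² for growth, and baseline within 2.54-17.78 mm² (Protocol 4.1.1). Assumed, because the documents do not give them: baseline uniform, or log-normal with median 7.2 and log-SD 0.5; linear growth; measurement-error SD 0.2 to 0.6 mm². The model is a repeated-measures fit at Weeks 24, 36 and 48 with unstructured covariance, complete data and 600,000 simulated patients per case. The table gives the reduction in the Week 48 standard error compared with leaving baseline out (linear baseline / log baseline).

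| Growth and baseline area | One baseline coefficient | Baseline by visit |
|---|---|---|
| Correlation 0 | 2-10% / 2-13% | 10-14% / 12-18% |
| Correlation 0.3 | 1-5% / 1-6% | 3-7% / 4-8% |
| Correlation 0.5 | 0-2% / 0-3% | 0.5-3% / 0.6-3.5% |
| Proportional | 0-1% | 0-1% |

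Under linear growth the dependence on baseline at Week 24 is half that at Week 48, and one coefficient for all visits cannot follow it. At error SD 0.2 the single coefficient recovers only 2-3% even at correlation 0.

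A second check used a truncated-normal baseline (location 8, scale 4, same limits). In a single-visit regression, adding baseline cut the SE by about 13% with growth independent of baseline (2.079 to 1.814 percentage points; power 70% to about 81%). The cut was 4-5% with growth following the square root of area and 0-1% with proportional growth. In a three-visit model with 13-14% dropout unrelated to baseline, one coefficient gave 1 − 1.89/2.04 = 7% and 1 − 1.59/1.65 = 4% in the first two settings.

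**3. Estimate and type I error.** With complete data and no true effect, the model without baseline rejected in 4.6-5.6% of trials (nominal 4.96%). With about 15% dropout, either unrelated to baseline, related to it equally in both arms, or related to it in the active arm only, rejection was 3.8-5.8% with or without baseline. With 400 trials per setting, one simulation SE is √(0.05 × 0.95/400) = 1.1 percentage points. With and without baseline, mean estimates in the three-visit model differed by at most 0.02 percentage points.

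**4. Growth slope.** Generalised least squares at Weeks 0, 24, 36 and 48, complete data: covariate main effects that remove 30% of the intercept variance change the slope-difference variance by 0%.

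For a sex-by-time term, Protocol 3.3.2.1 gives Month 18 mean changes of 3.831 mm² (women) and 2.310 mm² (men).

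- Difference: 3.831 − 2.310 = 1.521 mm². Scaled linearly to 48 weeks: 1.521 × 48/78 = 0.936 mm².
- Variance due to sex with a 50:50 split: 0.25 × 0.936² = 0.219.
- Protocol 6.1 reads "Assuming a standard deviation of 2.51 mm² for the change from baseline in GA area at 1 year in biomarker-positive patients" and uses 1.68 mm² for biomarker-negative patients. Both come from Phase II, since "sample size and power calculations used assumptions based on results from the Phase II Study CFD4870g" (SAP 2.3.1). SAP 2.3.2 uses 1.53 mm² from Study GX29633.
- Share of variance: 0.219/2.51² = 3.5%; 0.219/1.68² = 7.8%; 0.219/1.53² = 9.4%.
- Interval narrower by 1 − √(1 − share): 1.8%, 4.0% and 4.8%.

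Combining the two groups' 80% intervals gives a Month 18 difference of 0.82 to 2.22 mm². The share then runs from 1.0% (SD 2.51) to 19.9% (SD 1.53), and the interval is about 0.5% to 10.5% narrower. With 60% women the point shares are 3.3%, 7.5% and 9.0%. A separate simulation with a binary covariate shifting the slope by 0, 0.5, 1.0 and 1.5 mm²/year gave SE ratios of 1.00, 0.99, 0.95 and 0.87.

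**5. Reading speed.** The documents give no SD or baseline distribution, so no figure can be given.

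**The case against.** Leaving baseline out of a ratio-to-baseline outcome is stated in two places and looks like a deliberate convention. Nothing is contradictory or invalid. The analyses are supplemental or exploratory, and baseline-adjusted views of GA area are already planned. All of that stands, and it sets the weight of the point.

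The sentence at issue removes baseline as the primary model has it, with no baseline-by-visit term. What it costs by itself is therefore the one-coefficient column. The by-visit gain goes beyond the primary specification and makes a supplemental model more elaborate than the primary one. This stands too, and the two columns should be read separately.

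The SAP adjusts for baseline GA area, plans subgroups on it and adds a square-root analysis, so its authors seem to expect growth to depend on lesion size. Correlation 0, which gives the largest gains, then deserves the least weight. The sex figures come from small subgroups that Protocol 3.3.2.1 says to read with caution, and the 9.4% share divides a Phase II difference by an SD from another study.

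Finally, a statement of no bias and no type I error effect depends on missingness. One contrived pattern, with dropout related to baseline in opposite directions in the two arms, gave 6.8-9.2% rejection without baseline and 7.5-9.2% with it. In the planned repeated-measures form, adding baseline as a main effect does not cure that, so it is not an argument for or against the change. None of these points gives a reason to keep the omission.

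**Conclusion.** The point holds, as a minor improvement. The percent-change models omit a collected baseline value without the proportionality that would make the omission harmless, and the slope model gives its covariates no route to the growth rate.

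The consequence is possible loss of precision. For percent change in GA area it is 0-10% of interval width (0-13% with log baseline) for the omitted covariate as the primary model specifies it, and 0-14% (0-18%) with a by-visit term. For the slope it is about 2-5% at the Phase II sex difference. Gains at correlations of 0.3 to 0.5 are small, and the low end is zero. These sizes rest on an assumed baseline distribution, growth relation and measurement error. The treatment estimate is essentially unchanged under randomisation, given dropout that does not depend on baseline in opposite ways by arm. No confirmatory conclusion is affected.

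**What to change.** - **Percent change in GA area:** include baseline GA area, preferably on the log scale, with a baseline-by-visit interaction. A main effect alone is better than none but may recover little.
- **Percent change in reading speed:** include baseline reading speed with a baseline-by-visit interaction.
- **Growth slope:** add covariate-by-time terms, at least sex by time.

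The square-root analysis needs no change, because it already keeps baseline GA area. The cost is a few lines of SAP text and a few degrees of freedom; all values are already collected. The wording should be settled before Sponsor unmasking for the Week 48 analysis, so that the added terms cannot appear data-driven.
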